Improved access to precise measurement of capillary refill time will help expand the capabilities of experienced providers who are treating patients remotely through telehealth or less experienced providers treating patients in remote locations. This is especially important in low-resource settings or regions remote from specialty centers where providers may not be as experienced in the care of children. Triaging care for conditions such as pediatric dehydration is challenging due to lack of resources, especially in developing countries. However, even in well-developed nations, access to specialized care for pediatric patients is still lacking. Pediatric specialized care in the United States is largely regionalized. Most seriously ill children present first to community hospitals where resources and expertise to treat these children may be limited. In fact, more than 90 percent of emergency department visits for children in the United States are to non-specialty facilities (11). Admission rates for large specialty pediatric hospitals are 2-4 times larger than general emergency departments suggesting that the majority of providers caring for children have limited experience in treating higher acuity pediatric conditions (12). Additionally, in the setting of rising health care costs, many parents and other non-professional caregivers are increasingly seeking health information from non-traditional sources such as mobile smartphones.

- 2.1 Preliminary Data: A pilot study is ongoing on healthy adult volunteers. This study is not yet published in a peer-reviewed journal. The study's main objective is to compare CRT measured from Cap App versus manual visual assessment under differing temperature controls. The study has enrolled 19 participants, age 20-34; 9 female, 10 male. There is some variance in skin tone. We controlled for 5 temperature conditions (30°C, 27.5°C, 25°C, 22.5°C, 20°C) utilizing an ice bath to determine variance of CRT measurement under progressively colder temperatures. The results show that Cap App measures a longer CRT with greater variance in relation to the colder temperatures. It tends to overestimate CRT for darker skin tones. Overall, CRT is longer for Cap App than for a correlated, manual CRT measurement.

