4.0 Study Intervention(s)/Investigational Agent(s)

- 1.2 **Description:** Cap App – mobile smartphone application used to measure CRT. The CapApp is a smartphone mobile application created through a partnership with the University of Washington, The University of Toronto, and The University of Minnesota. Management of the application will primarily be the responsibility of The University of Washington Ubiquitous Computing Lab led by [name] and PhD candidate, [name]. Oversight of the project will be from The University of Toronto Assistant Professor of Computer Science, [name]. A standard Android smartphone running a custom smartphone application will be used for collecting fingertip videos, motion data, demographics (e.g., age, sex, temperature), and skin tone using the Fitzpatrick skin color scale. The app will start up and allow the user to enter a study ID and age, sex, race, skin tone, skin temperature, room temperature, core temperature, weight, vital signs (heart rate, blood pressure) and any underlying diagnosis. No other identifying information will be stored, including date of birth, name, audio, or fingerprint. The user is asked to place their right index finger on the

MEDICAL PROTOCOL (HRP-590)

PROTOCOL TITLE: Capillary Refill Time Measurement Utilizing Mobile Application (Cap App) in Children
VERSION DATE: 10/27/2022

front camera. Once the app confirms that the finger is correctly placed, it asks the user to apply pressure against the phone. When the app detects whether the user is applying enough pressure for the specified time, it asks the user to relax the pressure. A function to notate any required assistance for the child in pressing on the smartphone to measure the capillary refill will also be noted. This will be needed especially for younger children and infants as it may cause a difference in how to interpret the results of the measurement. The app collects accelerometer/gyroscope data and video recording of the fingertip. The fingertip recording will not collect fingerprint identification information. The collected data will be uploaded to the cloud server on a secure data storage platform, Box.

The device, as used in this study protocol, does not meet the criteria of a serious risk device under 21 CFR 812.3(m) and therefore is a non-significant risk (NSR) device. The device meets the criteria of a NSR-IDE for the following reasons:

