15.0 Statistical Considerations

15.1 Data Analysis Plan: We plan to utilize a Biostatistical Design and Analysis Center biostatistician from the Clinical and Translational Science Institute in the statistical analysis of our data. We will compare the manual method of CRT (human annotation with a stopwatch and computer analysis) and Cap App measurement of CRT amongst each individual subject. We will then create a normal range of Cap App CRT based on

MEDICAL PROTOCOL (HRP-590)

PROTOCOL TITLE: Capillary Refill Time Measurement Utilizing Mobile Application (Cap App) in Children
VERSION DATE: 10/27/2022

age of the subject in one of five categories (1-3 months, 3-12 months, 1-5 years, 5-12 years, and 12-17 years), sex (male or female), and race (skin tone). We will include a description of the primary diagnosis, vital signs (heart rate, blood pressure, oxygen saturation), temperature (room, patient core, and skin), and second, third, and fourth measurements of CRT (used for intra-rater reliability). Missing data will be documented as noted and the record will be excluded from analysis as applicable. Minimal missing data is expected, so missing data will not be imputed.

15.2 Power Analysis: The goal of this study is to determine the precision of the capillary refill time measured via the smartphone application, so no formal power calculation was performed.

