15.3 Statistical Analysis: We will recruit pediatrics patients aged 1 month to 17 years who are presenting to the D2D: The Driven to Discover Research Facility at the Minnesota State Fair. Descriptive statistics will be used to summarize the data collected. For the primary outcome, we will calculate mean CRT along with 95% confidence intervals, both overall and by age group, sex, and skin tone. We will attempt to enroll a minimum of 48 patients per age group for a total of 240 patients. Initial results showed an average standard deviation of 0.663 seconds across all patients at normal hand temperature. When the sample size is 48, a two-sided 95% confidence interval for a mean will extend ± 0.188 seconds. For a total sample size of 240, a two-sided 95% confidence interval for a mean will extend ± 0.084 seconds. Human annotation of a video recording using a stopwatch will be used to measure the manual CRT measurement and we will perform computer annotation of the video recording as a gold standard. For human and computer annotations we will calculate inter-rater reliability by repeating annotations with a different observer on 10% of a random group of CRT measurements. Inter-rater reliability will be evaluated using intraclass correlation coefficients (ICCs) and Bland–Altman plots.

15.4 Data Integrity: The research assistant will obtain study eConsent and fill the data collection forms which will be embedded into the Cap App and will be password protected. The data forms, video recordings for human and computer annotation, and Cap App CRT measurement will then be uploaded to a secure web-based data storage platform, Box. The research assistant will erase the data on the smartphones every shift and will store them in a secure location at all times. The *consent forms, assent forms, and case report forms* will be electronic (UMN REDCap eConsent). No paper copies will be utilized.

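### Cap App normal values rest on five separate age bands with no model of age; a small pre-specified smooth-age regression beside the bands would serve section 3.2 better, with a modest average gain in precision

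*Combined protocol and SAP*

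**What the plan says.** Section 15.1 (Data Analysis Plan) will create the normal range by "age of the subject in one of five categories (1-3 months, 3-12 months, 1-5 years, 5-12 years, and 12-17 years", by sex, and by race (skin tone). Section 15.3 (Statistical Analysis) summarises the primary outcome as mean CRT with 95% intervals, overall and by age group, sex and skin tone.

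The sample size follows the bands: "We will attempt to enroll a minimum of 48 patients per age group for a total of 240 patients". Precision is then given for one band, "When the sample size is 48, a two-sided 95% confidence interval for a mean will extend ± 0.188 seconds", and for the whole sample: "For a total sample size of 240, a two-sided 95% confidence interval for a mean will extend ± 0.084 seconds". The SD behind both is introduced with "Initial results showed an average standard deviation of 0.663 seconds across all patients at normal hand temperature". No regression on age, or on any other characteristic, is specified.

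Section 3.2 has wider secondary outcomes: normal values across age ranges, and whether skin tone, skin temperature, sex or age affects Cap App CRT. The data needed are collected. Section 4.0 (Description) says the app will "allow the user to enter a study ID and age, sex, race, skin tone" and also skin temperature. It does not store date of birth and gives no unit for age.

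**The concern.** Three things follow from using bands alone.

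- **Within a band, age is ignored.** A child just over 5 and one of nearly 12 get the same normal value, and so do a child just over 1 and one of nearly 5.
- **At a band edge, the value jumps.** Two children a few weeks apart in age can be judged against different normal values only because a cut point lies between them.
- **The effects asked about in section 3.2 stay entangled.** Separate summaries by age group, sex and skin tone cannot show whether a difference between age groups reflects age or a different mix of skin tones and sexes. Sections 8.3 and 11.1 describe a convenience sample, and section 10.1 only attempts to match on age group and skin tone.

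Section 2.2 names normative Cap App values as the study's aim, for later use in detecting abnormal perfusion. Each band's mean uses about 48 children and takes nothing from neighbouring ages.

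**Working it through.** **Inputs.** SD 0.663 s, n = 240 and 48 per band (section 15.3); 1.96 for two-sided 95%.

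**Assumptions.** 48 children spread evenly within each band; top band run to the 18th birthday; constant SD; six skin-tone types (section 4.0 names the Fitzpatrick scale but not the number of types).

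**1. The plan's own figures.**
- 1.96 × 0.663 / √48 = 0.188 s
- 1.96 × 0.663 / √240 = 0.084 s

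Both reproduce.

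**2. Average precision of an age-specific mean.** In a least-squares fit with p mean parameters, the squared standard error averages SD² × p/240 over the 240 children. The root-mean-square (RMS) half-width is therefore 1.96 × 0.663 × √(p/240). Five bands are p = 5.

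| Age model | p | RMS half-width | Against bands |
|---|---|---|---|
| Five bands | 5 | 0.188 s | – |
| Spline, 4 knots | 4 | 0.168 s | 1 − √(4/5) = 11% narrower |
| Spline, 3 knots | 3 | 0.145 s | 1 − √(3/5) = 23% narrower |
| Spline, 5 knots | 5 | 0.188 s | no gain |

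The percentages do not depend on the SD.

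**3. Precision at particular ages.** Restricted cubic spline in log age, half-width = 1.96 × SD × √(x′(X′X)⁻¹x):

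| Age | 3 knots | 4 knots | Band mean |
|---|---|---|---|
| 1 month | 0.244 s | 0.299 s | 0.188 s |
| Five band midpoints | 0.110-0.168 s | 0.133-0.176 s | 0.188 s |
| Near 18 years | 0.181 s | 0.218 s | 0.188 s |

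**4. With sex and skin tone in both models.** Sex adds 1 parameter and six skin-tone types add 5. The splines then have p = 3 + 6 = 9 and 4 + 6 = 10, and the bands 5 + 6 = 11. RMS half-widths for a mean specific to a child's age, sex and skin tone are 0.252, 0.265 and 0.278 s. The gain is 1 − √(9/11) = 9.5% or 1 − √(10/11) = 4.7%. With skin temperature added to all three (p = 10, 11, 12) it is 8.7% or 4.3%.

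**5. Normal limits.** For the 97.5th centile under normality, half-width = 1.96 × SD × √(v + 1.96²/(2 × df)), where v is 1/48 for a band and p/240 on average for a curve.
- Bands, each with its own SD (df 47): 0.323 s
- Bands, pooled SD (df 235): 0.221 s
- 4-parameter curve (df 236): 0.205 s
- 3-parameter curve (df 237): 0.187 s

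Pooling the SD supplies 0.323 − 0.221 = 0.102 s of the total fall. That is 0.102/0.136 = 75% for the 3-parameter curve and 0.102/0.118 = 86% for the 4-parameter curve.

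**6. Size of the steps.** The documents give no age effect, so this is illustration only. Suppose mean CRT changes by 0.2, 0.5 or 1.0 s in total from 1 month to 18 years, in a straight line on raw or log age. A band mean is then off at a band edge by up to 0.039, 0.098 or 0.195 s, and neighbouring band means differ by up to 0.073, 0.181 or 0.363 s.

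**The case against.** The study is descriptive and sized for precision. Its recruitment targets, sample size and intervals are all built on the same bands, its stated precision reproduces, and a banded table is a usable reference format. Nothing planned is invalid. A curve brings its own assumption, that the chosen shape is right, and with five parameters the average gain disappears. All of this stands, and it is why the bands should stay.

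The loss of precision at the ends of the age range also stands, with one qualification. The band interval at 1 month looks narrower because it estimates the 1-3 month average and treats a 1-month-old as equal to it.

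A reader might infer more than the documents support:

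- **That age is the main driver of normal CRT.** Section 2.0 names age and sex together and ranks neither. Section 3.2 lists age as one of four characteristics. The pilot in section 2.1 reports temperature and skin-tone effects.
- **That a curve is clearly more precise at every age, or reaches ±0.084 s.** Steps 2 to 4 show a modest average gain that reverses at the extremes.
- **That ±0.188 s is the precision of the normal limits.** It is the precision of a mean; limits are less precise (step 5).
- **That the plan needs 5 × 2 × 6 = 60 cells of 4 children each.** Section 15.1 could be read so, but section 15.3 reads more naturally as separate summaries by each factor, and the 48-per-band sizing fits that.
- **That the pilot shows CRT must be logged.** The statement "Cap App measures a longer CRT with greater variance in relation to the colder temperatures" describes adults in an ice-bath experiment. It says nothing about spread by age or skewness at normal hand temperature.

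**Conclusion.** The point holds as a cheap improvement. Sections 15.1 and 15.3 give age-specific values only within bands, and they contain no analysis that separates age from sex, skin tone or skin temperature as section 3.2 needs. A smooth-age regression with 3 or 4 age parameters would do so without steps at the cut points.

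The precision gain is secondary: on average 11-23% for a mean averaged over sex and skin tone, and about 5-10% for child-specific means with sex and six skin-tone types in both models. For normal limits most of the gain comes from pooling the SD, which a banded analysis could also do.

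These results assume an adequate curve, additive effects, constant SD and the target of 48 per band being met with even spread. The half-widths in seconds scale with 0.663 s. Section 15.3 does not name the source of that SD, and the only pilot described is in adults: "The study has enrolled 19 participants, age 20-34; 9 female, 10 male". The real size of the steps cannot be derived from the documents.

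**What to change.** Keep the five bands for recruitment and display. Add to section 15.1, before the CRT values are analysed:

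- One regression of Cap App CRT on a restricted cubic spline of log age (3 or 4 parameters including the intercept, knots stated), with sex, skin tone and skin temperature as additive terms.
- Normal limits from the residual SD, after checking whether the SD varies with age and whether a log scale for CRT is needed.
- Fitted means and limits at each band midpoint, with a note that intervals widen at the ends of the age range.
- Age in completed months, or weeks under 1 year. This version is dated after the recruitment dates in section 8.3, so for children already enrolled the plan should state the unit in which age was stored.

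The cost is SAP wording, a little more analysis and a fixed unit for the age field. The price in the results is dependence on the chosen curve, and wider intervals at 1 month (about ±0.24 to ±0.30 s) and, with 4 parameters, near 18 years (about ±0.22 s). No extra enrolment is needed.

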3.0 Study Endpoints/Events/Outcomes

- 3.1 Primary Endpoint/Event/Outcome: Determining the accuracy and precision of a mobile health application (Cap App) to measure CRT in an otherwise healthy pediatric patient population.
- 3.2 Secondary Endpoint(s)/Event(s)/Outcome(s): To establish normal values of CRT via Cap App for healthy children of varying age ranges, determine if subject characteristics such as skin tone, skin temperature, sex, or age affect the CRT measured via the Cap App, and determine if the CRT measured via the Cap App correlates to the manual measurement of CRT in healthy children at varying age ranges.

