- a. Demographics (race/ethnicity, gender, age).
- b. Temperature (environment, core, skin at finger).
- c. Clinical (weight, blood pressure, heart rate, oxygen saturation, skin tone)
- d. CRT measurement (manual video, Cap App)
- e. Any underlying diagnosis (medical history)

5.2 Study Duration:

- Total study length: 15 months including 3 months for protocol development and IRB approval, 6 months for data collection, and 6 months for data analysis.
- Individual participant: time expected to complete the study is 30 minutes; 20 minutes for enrollment screening and consent and 10 minutes for the CRT measurements

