7.2 Sharing of genetic testing: NA

8.0 Study Population

8.1 Inclusion Criteria: Healthy children aged 1 month – 17 years.

8.2 Exclusion Criteria:

- Fever or hypothermia
- Chronic illness including cardiovascular or renal disease
- Severe injury or blood loss

MEDICAL PROTOCOL (HRP-590)

PROTOCOL TITLE: Capillary Refill Time Measurement Utilizing Mobile Application (Cap App) in Children

VERSION DATE: 10/27/2022

- Dehydration (including vomiting and/or diarrhea)
- Raynaud's phenomenon
- Children who do not have a parent or legal guardian present to obtain consent

8.3 Screening: Convenience sample of participants presenting at the D2D: The Driven to Discover Research Facility at the Minnesota State Fair August 25 - September 5, 2022 will be screened for inclusion and exclusion criteria. All those who are eligible will have the opportunity to enroll. We will utilize a script to assist in the screening process to ensure that all information is presented accurately and uniformly to all potential participants.

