12.0 Withdrawal of Participants

12.1 Withdrawal Circumstances:

Participants are free to withdraw from participation in the study at any time upon request. An investigator may discontinue or withdraw a participant from the study for the following reasons:

- If any clinical adverse event (AE), or other medical condition or situation occurs such that continued participation in the study would not be in the best interest of the participant. This may include if there are any signs of discomfort (i.e. crying, tantrums, fits, screaming).
- If the participant meets an exclusion criterion (either newly developed or not previously recognized) that precludes further study participation

12.2 Withdrawal Procedures: If a participant/parent/guardian wishes to withdraw or we determine that the participant should withdraw, we will terminate data collection and discuss with the participant the reasons for withdrawal. All data collected up to that point will be used in analysis. This will be made known in the consent form.

12.3 Termination Procedures:

This study may be temporarily suspended or prematurely terminated if there is sufficient reasonable cause. Written notification, documenting the reason for study suspension or termination, will be provided by the suspending or terminating party to the funding agency. If the study is prematurely terminated or suspended, the PI will promptly inform the IRB and will provide the reason(s) for the termination or suspension. The study team will notify the participants of the study termination.

Circumstances that may warrant termination or suspension include, but are not limited to:

- Determination of unexpected, significant, or unacceptable risk to participants
- Demonstration of efficacy that would warrant stopping
- Insufficient compliance to protocol requirements
- Data that are not sufficiently complete and/or evaluable
- Determination that the primary endpoint has been met
- Determination of futility

The study may resume once concerns about safety, protocol compliance, and/or data quality procedures are addressed and satisfy the sponsor, IRB and/or FDA.

MEDICAL PROTOCOL (HRP-590)

PROTOCOL TITLE: Capillary Refill Time Measurement Utilizing Mobile Application (Cap App) in Children
VERSION DATE: 10/27/2022

Data collected for the study prior to the study termination will be handled in the following manner:

- If the study is terminated due to safety reasons, the data related to AEs will be evaluated.

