21.0 Consent Process

21.1 Consent Process (when consent will be obtained):

Participants will self-report with interest at the D2D: The Driven to Discover Research Facility at the Minnesota State Fair.

- The consent will take place in the research space provided at the D2D: The Driven to Discover Research Facility.
- There is no built-in waiting period available between informing the prospective participants and obtaining the consent. If the subject requests a waiting period to help make an informed decision, a reasonable time will be allotted to accommodate that request as deemed appropriate by the treating provider.
- We will provide a copy of the current ICF to the participant, in advance if possible.
- ICF will be read to the participant after which questions will be invited and responded to.
- The participant will be given time to discuss consent with others, including taking ICF home to consider.
- The researcher will determine if the potential participant understands the information presented through the consent process and

MEDICAL PROTOCOL (HRP-590)

PROTOCOL TITLE: Capillary Refill Time Measurement Utilizing Mobile Application (Cap App) in Children

VERSION DATE: 10/27/2022

comprehends study details. It is under the discretion of the researcher, and per D2D requirements, that if there is suspect of alcohol intoxication, consent will not proceed at that time.

- We will obtain consent from one parent/legally authorized representative and assent from the participant if old enough.
- This will be obtained by electronically in-person utilizing the D2D provided devices (i.e. iPads) with electronic signature capture.
- An electronic copy of the signed ICF/HIPAA forms will be emailed to the participant.
- We will ensure ongoing consent through voluntary participation in the study including performing the procedure. We will ensure voluntary participation at each stage of the study through verbal confirmation.

21.2 Waiver or Alteration of Consent Process (when consent will not be obtained): NA

21.3 Waiver of Written/Signed Documentation of Consent (when written/signed consent will not be obtained): A script will be used to screen potential participants for enrollment, prior to obtaining consent. This script will ensure that all information is presented accurately and uniformly to all potential participants. No PHI or study procedures will occur until formal consent process is conducted and signed consent/assent is provided.

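### Section 12.2 keeps readings from children withdrawn for meeting an exclusion criterion in an analysis meant to describe healthy children

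*Combined protocol and SAP*

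**What the plan says.** Section 3.2 gives as a secondary aim "To establish normal values of CRT via Cap App for healthy children of varying age ranges", and section 8.1 restricts entry to healthy children. Section 8.2 lists the exclusions, among them "Fever or hypothermia".

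Section 12.1 names two grounds on which an investigator may withdraw a child. The second reads: "If the participant meets an exclusion criterion (either newly developed or not previously recognized) that precludes further study participation". Section 12.2 covers withdrawal by the family and withdrawal decided by the study team, and gives one data rule for both: "All data collected up to that point will be used in analysis".

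In the analysis plan, section 15.1 has a single exclusion rule: "Missing data will be documented as noted and the record will be excluded from analysis as applicable". It adds that missing data are expected to be minimal and will not be imputed. Section 15.3 plans mean CRT with 95% confidence intervals overall and by age group, sex and skin tone, with at least 48 children in each of five age groups. Neither section defines an analysis set by eligibility.

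**The concern.** The two rules serve different purposes and meet badly in one case. Keeping data up to withdrawal is sensible for an eligible child who stops because of crying or at a parent's wish. For a child withdrawn because he or she should not have been enrolled, the same rule keeps a reading from outside the population the study describes.

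A normal range is only as good as the definition of who is normal. If ineligible children stay in, the range and the comparison with the manual method no longer describe the group named in 3.2 and 8.1. If the team instead drops such children when it meets them, it departs from 12.2 without a written rule. That decision could then be taken after the CRT values are known.

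**Working it through.** **Step 1: does any other text remove these children?** 12.1 supplies the withdrawal reason. 12.2 applies its data rule to every withdrawal. The exclusion in 15.1 is triggered by missing data, and a complete set of readings from an ineligible child has nothing missing. No other analysis text excludes by eligibility, so the readings stay in.

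**Step 2: can it happen?** Screening uses a script before consent (8.3, 21.3). The data to be collected in 5.1 include "Temperature (environment, core, skin at finger"), and 21.3 says: "No PHI or study procedures will occur until formal consent process is conducted and signed consent/assent is provided". A measured core temperature therefore becomes available only after consent. The protocol does not say whether it is taken before or after the CRT readings. A temperature exclusion could be recognised when readings already exist.

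**Step 3: the plan's own precision figures.** Inputs from 15.3: SD 0.663 s, n = 48 and n = 240.

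- 1.96 × 0.663 / √48 = 0.188 s
- 1.96 × 0.663 / √240 = 0.084 s

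Both agree with the protocol.

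**Step 4: size under stated assumptions.** The protocol gives neither the number of such children, nor how far their readings differ, nor the method for the normal range. Assume k children in a group of n read d seconds high on average, with d = 0.5, 1 or 2 s, and put p = k/n.

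- Shift in mean = p × d
- New SD = √(0.663² + p(1 − p)d²)
- Shift in mean + 1.96 SD = p × d + 1.96 × (new SD − 0.663)

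Example, k = 1, n = 48, d = 2: the mean shifts by 2/48 = 0.042 s; the new SD is 0.722 s; the limit shifts by 0.042 + 1.96 × 0.059 = 0.157 s.

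If the upper limit is the 97.5th percentile, the result depends on the convention. Rank 0.975 × 49 = 47.8 and rank 1 + 0.975 × 47 = 46.8 are both in common use. The expected shifts come from 200,000 simulated normal samples of 48.

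| Shift in seconds, n = 48 | d = 0.5 | d = 1 | d = 2 |
|---|---|---|---|
| Mean, one child | 0.01 | 0.02 | 0.04 |
| Mean + 1.96 SD, one child | 0.02 | 0.05 | 0.16 |
| 97.5th percentile, one child | 0.02 | 0.06 to 0.10 | 0.19 to 0.53 |
| Mean + 1.96 SD, two children | 0.04 | 0.10 | 0.30 |
| 97.5th percentile, two children | 0.04 to 0.05 | 0.13 to 0.18 | 0.53 to 0.84 |

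With all 240 children, one such child moves mean + 1.96 SD by 0.004, 0.010 or 0.033 s. Readings low by the same amounts would move the mean and the lower limit down equally.

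**Step 5: yardstick.** The standard error of mean + 1.96 SD at n = 48 is about 0.663 × √(1/48 + 1.96²/(2 × 47)) = 0.165 s, or about ±0.32 s at 95%. The one-child shifts in that limit are smaller than this standard error. The one-child shifts in the mean are well below ±0.188 s.

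**The case against.** The strongest reply is that the case is close to hypothetical. Children are screened by script against the criteria before consent, each has a single visit, and the CRT measurements take about 10 minutes (5.2), so there is little time for a criterion to develop. If no child is affected, no result changes. This stands as a limit on size. It does not remove the conflict: 12.1 itself foresees a criterion not recognised earlier, and 12.2 says what then happens to the data.

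A reader might go further in four ways that the documents do not support.

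- *That such readings would raise the upper limit.* Section 2.1 does say "The results show that Cap App measures a longer CRT with greater variance in relation to the colder temperatures". But that pilot cooled healthy adult volunteers with an ice bath. It does not show what a hypothermic child's reading would be, and it says nothing about fever.
- *That 12.2 contradicts 13.1.* Section 13.1 lets families have video recordings redone or deleted. A deleted recording is no longer held, so the two sections can coexist.
- *That the app's developers decide which readings are usable.* No section says so. Section 4.0 has the app check placement and pressure at capture, 15.1 plans a biostatistician from the institute, and 5.1 has a separate blinded annotator for the videos.
- *That the plan has no handling of missing readings.* Section 15.1 documents missing data and assigns the second to fourth readings to reliability, which implies that the first is the main one. What remains is missing detail.

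**Conclusion.** The concern holds in this form: 12.1, 12.2 and 15.1 together direct that readings from children the protocol classes as ineligible enter the analysis of healthy children, and nothing else in the protocol removes them. This rests on the text alone.

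The likely numerical effect is small. Group means hardly move. A group's upper limit could move noticeably only if an ineligible child's reading lay far from the rest and the limit were a sample percentile; even then the figure depends strongly on the percentile convention. All shifts rest on assumed differences of 0.5 to 2 s and on an SD of 0.663 s. Neither the count nor the direction comes from the documents. The stated half-widths of ±0.188 s and ±0.084 s are correct.

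The correction is worth making because it costs little and fixes in advance who belongs in a healthy reference range.

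**What to change.** State in 12.2, and repeat in 15.1:

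> *Readings from eligible children who withdraw are used. A child found after consent to have met an 8.2 exclusion criterion at the time of measurement is listed with the reason and left out of the means, normal ranges and method comparison. This is decided without sight of the CRT values.*

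The phrase about the time of measurement matters: a reading taken before a criterion arose stays in.

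Cost: wording, plus a short eligibility check by someone blind to the readings. Children left out no longer count towards 48 per age group. On the stated dates, recruitment (25 August to 5 September 2022) closed before this version (27 October 2022), so the change affects only the analysis. It should be fixed before Cap App and manual values are compared; if that has already happened, the report should say so.

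Two minor notes: state whether the first usable reading or the child's average enters the mean, and report the number of children with no Cap App result by age group. The choice not to impute can stay.
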